2.2.2. Secondary

The secondary objectives are to evaluate the efficacy of RZL-012 subcutaneous injections in the submental area, relative to placebo by:

- Evaluation of treatment efficacy by using Physician's global assessment questionnaire, on study Days 28, 56, and 84
- Reduction from baseline in submental fat volume, as measured by MRI
- Improvement in subject's satisfaction rating score of the FACE-Q questionnaire on study Days 28, 56, and 84 vs. baseline

3. STUDY DESIGN

3.1. DESCRIPTION OF STUDY DESIGN

This is a single blinded, randomized, placebo-controlled, 2-cohort, clinical study in healthy volunteers.

Cohort 1 will be comprised of 8 active (RZL-012) and 4 placebo subjects. Cohort 2 will be comprised of 16 subjects. That will be randomized to receive active or placebo treatment All subjects will receive a single dose of RZL-012 or vehicle into the submental fat, after which they will be monitored for safety and efficacy assessments across 84 days of follow-up. All subjects per cohort will be randomized to either active treatment or placebo at a ratio of 2:1 per cohort. Subjects will be blinded to study treatment while physicians will not be blinded.

The study will be composed of 2 treatment cohorts, 12 subjects at cohort 1 and 16 subjects at cohort 2.

A total of 28 subjects will be treated in 2 clinical sites.

At cohort 1, a total of 12 subjects will be randomized to receive active or placebo treatment (2:1) according to randomization program that will be prepared prior to study initiation. At cohort 2, 16 subjects will be randomized to receive active or placebo treatment. Each clinical site will have at least one active and one placebo treatment subject per each study cohort. In case of slow enrollment in one of the sites, other sites may complete the enrollment of subjects in each cohort.

3.2. DOSE RATIONALE

In all previous clinical trials, the maximal RZL-012 dose per injection site was 5 mg, and a distance of 2-3 cm or 1 cm between injection points was maintained. The total overall RZL-012 dose tested to date was 180 mg, which is 75% of the NOAEL. No serious adverse events were associated with this dose per injection site, with the distance maintained between injection sites or with the maximal overall dose.

Thus, for the current trial, the starting dose of a maximal 120 mg has been chosen based on a dose of 2.5 mg per injection site, a distance of 1 cm between injection columns and rows of the submental pattern and on an estimation of the dimensions of the submental area. A distance of 1 cm will allow a good distribution RZL-012 into the submental area.

To increase the potential to demonstrate efficacy, a higher RZL-012 dose of a maximal 240 mg will also be assessed, on condition that no serious safety concerns are raised within 28 days of follow-up post-dose of 12 subjects having received the starting dose. To achieve this maximal dose, the 5 mg dose per injection site will be used with the same pattern of submental fat grid (i.e., 1 cm between injection columns and 1 cm between injection rows). The number of injections will be determined by the physician based on the fullness of submental fat. Upon review of initial safety data in subjects receiving the lower dose, sponsor may or may not decide to increase the dose as planned for remaining subjects.

3.3. DOSING

3.3.1. Dosing Regimen

All subjects will receive a single dose of RZL-012 or placebo in multiple injections, in accordance with the treatment cohorts as shown in Table 2 below.

RZL-012-SMF-P2US-001 Version: 1.2

Table 2: Study Design

[figure not shown]
	N=28		
	Cohort 1 N=12	Cohort 2 N=16	
Number of RZL-012/Placebo	8/4	At least 4 placebo subjects	
Total Maximal Dose RZL-012 (mg)/vehicle (mL)	Up to 120 mg/2.4 mL	Up to 240 mg/4.8 mL	
Dose of RZL-012 (mg)/vehicle (mL) per single injection	2.5 mg/0.05 mL	5 mg/0.1 mL	
Maximal Number of Injections per subject	48	48	

Cohort 1 active subjects will receive a maximal dose of up to 120 mg RZL-012 in a series of up to 48 injections. Each injection point will be dosed with 2.5 mg RZL-012 (0.05 mL of RZL-012 solution). Placebo (vehicle) subjects will be injected with 0.05 mL vehicle at each injection site, resulting in a total volume of up to 2.4 mL.

Cohort 2 active subjects will receive a maximal dose of up to 240 mg RZL-012 in a series of up to 48 injections. Each injection point will be dosed with 5 mg RZL-012 (0.1 mL of RZL-012 solution). Placebo (vehicle) subjects will be injected with 0.1 mL vehicle at each injection site, resulting in a total volume of up to 4.8 mL.

The injection pattern in Cohort 1 and Cohort 2 will be based on a submental area shaped grid in which the distance between rows will be 1cm and distance between columns will also be 1 cm as seen in the figure below. Physician will choose two points at the edge of the 50-point pattern that will not be injected (up to 48 injections):

Figure 5: Scheme of Injection Pattern that will be used by the Physician to Inject into the Submental Fat Area in Both Study Cohorts

Twelve (12) subjects from Cohort 1 that will be enrolled in 2 clinical sites (8 active and 4 placebo) will be injected with a maximal dose of 120 mg/subject or with up to 2.4 mL of vehicle. If no serious safety concerns will be noted within 28 days of follow-up post-dose of subjects from Cohort 1, the study will proceed to the additional 16 subjects of Cohort 2. These subjects (that will be randomized to receive active or placebo treatment with at least 4 placebo subjects) will be injected with a maximal dose of 240 mg/subjector up to 4.8 mL vehicle.

Treatment of Cohort 2 will start following Cohort 1 Day 28 data. An independent Data Safety Monitoring Board (DSMB) will review the safety and tolerability data for Cohort 1 subjects, 28 days after injection, and decide whether it is safe to increase the dose for next study cohort. The decision to proceed to the Cohort 2 will be made within 30 days (28 days +2) after injection of the last dosed subject of Cohort 1.

The DSMB will be comprised of 2 independent MDs with expertise in the aesthetic area and in conduction of clinical trials.

In case of serious safety concerns (e.g., prolonged severe swelling or severe pain following injection) among Cohort 1 subjects receiving the 120 mg dose, sponsor and DSMB may decide to reduce or stay with the 120 mg/subject dose level for Cohort 2 subjects.

Subjects will be injected with RZL-012 or vehicle perpendicularly (90°) to the skin. An ice pack will be placed on the injected area for pain relief immediately after injection. Subjects will have to remain seated in the injection position for an additional 10 minutes after dosing.

3.3.2. Serious Adverse Events Considered Related to the Investigational Drug

The adverse events (AEs) and serious adverse events (SAEs) will be monitored throughout the study.

Study discontinuation is to be considered by the investigator in any case of SAEs and the actions taken are to be fully documented in source documents and Case Report Forms (CRFs).

SAEs are considered to be possibly or probably related to the study drug.

Subjects experiencing an SAEs will be followed for their skin condition.

SAE should be reported within 24 hours to the medical monitor.

The study may also be prematurely terminated in any of the following cases:

- Recurring serious or severe Adverse Drug Reaction (ADR) clinically evaluated by PI as warranting study termination.
- A decision made by Sponsor/medical monitor and/or IRBEC and/or local regulatory agency to terminate the study.

4. STUDY ENDPOINTS

4.1. PRIMARY ENDPOINTS

The main objective is to evaluate safety following injection of RZL-012 vs. placebo injection into submental fat. Skin irritancy and AEs related to injection procedure will be mainly evaluated for its frequency, severity and duration. Specifically, the assessment of the following AEs will be monitored: bruising, pain, induration erythema and swelling/edema.

In cohort 1a total of 12 subjects will be randomized to receive active treatment or placebo (2:1) and in cohort 2 16 subjects will be randomized (at least 4 placebo subjects will be randomized) in the 2 clinical sites. Each clinical site will have at least one active and one placebo at each study cohort.

Twelve (12) subjects from Cohort 1 (8 active and 4 placebo) will be injected with a maximal dose of 120mg/subject or with up to 2.4 mL of vehicle. If no serious safety concerns will be noted within 28 days of follow-up post-dose of subjects from Cohort 1 (e.g., prolonged severe pain or severe swelling following injection), the study will proceed to the additional 16 subjects of Cohort 2 that are designated to be injected with a maximal dose of 240 mg/subject for active treatment or up to 4.8 mL vehicle in 4 for at least 4 placebo subjects that will b randomized.

In case of serious safety concerns among subjects receiving the 120 mg dose, sponsor and DSMB review may decide to reduce or remain with the 120 mg/subject dose level for remaining subjects.

4.2. SECONDARY ENDPOINTS

Following are the study's secondary endpoints that evaluate treatment efficacy of active treatment vs. placebo subjects:

- 1. Improvement of Physician' global assessment questionnaire for treatment efficacy in active vs. placebo treated subjects on Days 28, 56, and 84 follow up visits to evaluate treatment response, see definition in Section 6.1.15.2.1.
- 2. Reduction from baseline in submental fat volume, as measured with MRI on Day 84 vs. screening, in RZL-012 treated subjects vs. placebo treated subjects, see definition in Section 6.1.15.2.2.
- 3. Improvement from baseline in Subject's satisfaction Rating by using validated FACE-Q questionnaire (Satisfaction of chin) on Days 28, 56, and 84 follow up visits to evaluate treatment response among RZL-012 treated subjects vs. placebo treated subjects, see definition in Section 6.1.15.2.3.

5. STUDY POPULATION

5.1. INCLUSION CRITERIA

Subjects meeting all of the following criteria will be eligible for study participation:

- 1. Men and women 18-65 years old, all in good health.
- 2. Subjects with Body Mass Index < 35 as determined at screening visit.
- 3. Subjects must have submental skin fold thickness greater than 1.5 cm as measured with calipers.
- 4. Males must be willing to be clean shaved for all study visits.
- 5. Patient weight must be stable (no fluctuation of >15 pounds in the past year).
- 6. Males or females in the age of fertility agree to use a double-barrier contraceptive device (e.g., condom and spermicide) for 4 weeks after treatment with RZL-012.
- 7. Subjects must be able to adhere to the visit schedule and protocol requirements and be available to complete the study.
- 8. Subjects must sign an IRB approved informed consent indicating they are aware of the investigational nature of the study.

5.2. EXCLUSION CRITERIA

Subjects meeting any of the following criteria will be excluded:

- 1. Unable to tolerate subcutaneous injection.
- 2. Pregnant or lactating women.
- 3. Subjects with dysfunctional gallbladder activity, e.g., underwent cholecystectomy or cholecystitis.
- 4. Any uncontrolled systemic disease -a potential patient in whom therapy for a systemic disease is not yet stabilized will not be considered for entry into the study.
- 5. Treatment with botulinum toxin injections in the neck or chin area within 6 months before screening.
- 6. Excessive submental skin laxity.
- 7. Any Scars, unshaven hair, tattoos or jewelry on or near the proposed treatment area.
- 8. Significant history or current evidence of a medical, psychological or other disorder that, in the investigator's opinion, would preclude enrollment into the study.

- 9. An active dermatitis or open wound in the proposed treatment area.
- 10. An active bacterial, fungal, or viral infection in the proposed treatment area.
- 11. Pre-existing skin condition to the submental region that may confound evaluation or analysis, at investigator discretion.
- 12. Previously treated with focused ultrasound, radiofrequency, cryolipolysis, liposuction, sodium deoxycholate to the submental region within the previous 6 months.
- 13. Pre-existing neurological or gastrointestinal condition leading to dysphagia, dysphonia or facial nerve palsy.
- 14. Pre-existing medical condition other than increased submental fat that may result in increased submental fullness such as but not limited to thyroid enlargement, goiter, cervical lymphadenopathy etc., at investigator discretion.
- 15. Must not have a planned fat reduction procedure of any variety to the submental region for the duration of the study.
- 16. Must not have planned significant alterations in diet or physical activity that may result in significant fluctuations in weight.
- 17. Subjects with medication or history of coagulopathy.
- 18. Allergic subjects to Benadryl.
- 19. Subjects treated chronically at least 3 months prior to study entry with systemic steroids or immunosuppressive drugs.
- 20. Subjects treated chronically at least one week prior to study entry with Non-Steroidal Anti-Inflammatory Drugs (NSAIDs).
- 21. Current participation or participation within 3 months prior to the start of this study in a drug or other investigational research study.
- 22. Claustrophobia or MRI incompatible device or implant.

5.3. SUBJECT IDENTIFICATION

At each site, a unique code numbers will be assigned by the investigator to the trial subject rather than the subjects' names, personal identification numbers, and/or addresses to protect the subject's identity. The code numbers and initials will be used in lieu of the subject's name when the investigator reports AEs and/or other trial related data.

5.4. REMOVAL, REPLACEMENT OR EARLY WITHDRAWAL OF SUBJECTS FROM ASSESSMENT NOT DUE TO INTOLERABLE SIDE EFFECTS

Subjects experiencing serious side effect will be withdrawn from the study, but followed until the event resolves or becomes stable. If a subject is withdrawn or removed from the study due to serious side effects, the subject will not be replaced.

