- 9. Immediately following completion injection of the submental fat, an ice/cold pack will be applied for immediate pain relief. It will be held by the subject for at least 2 minutes.
- 10. The physician will record the number of injections administrated for each subject, at each cohort.

In Cohort 1, the first 8 subjects randomly assigned to the RZL-012 treatment group will initiate at the dose of 2.5 mg (0.05 mL volume of RZL-012 solution) RZL-012 in a single injection (resulting in a total of up to 120 mg) in a series of maximum 48 injections. Additional 4 subjects will be given placebo (vehicle) in a volume of 0.05 mL in a single injection, resulting in a maximal volume of 2.4 mL injected into the submental area.

In Cohort 2, an additional 16 subjects randomly assigned to the RZL-012 treatment group will initiate at the dose of 5 mg (0.1 mL volume of RZL-012 solution) RZL-012 in a single injection (resulting in a total of up to 240 mg) in a series of maximum 48 injections, where at least 4 subjects will be given placebo (vehicle) in a volume of 0.1 mL in a single injection, resulting in a maximal volume of 4.8 mL.

The injection pattern that will be used in both cohorts will be based on existing grid in the shape of submental area, where distance between injection rows will be 1cm and distance between injection columns will be 1cm as seen in Figure 5, Section 3.3.1.

The amount of injections for each subject will be decided by the physician according to the fullness of submental fat.

In cases where the physician will have to inject a total number of 48 injections, the physician will choose two points in the edge of the grid pattern that will not be injected (The grid contains 50 injections points).

If no serious safety concerns will be noted by DSMB within 28 days of follow-up post-dose of subjects from Cohort 1, the study will proceed to cohort 2 where an additional 16 subjects will receive active treatment where at least 4 out of the 16 subjects will be injected with vehicle.

Each RZL-012 kit contains 1 vial (250 mg/5 mL) corresponding to the number of subjects receiving treatment in each cohort.

RZL-012 will be injected on Day 0 study visit (baseline).

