6.2.7. Termination Visit

Once study is discontinued, all reasonable measures should be taken to perform a termination visit. Termination visit should include all procedures necessary to complete subjects' records:

AE reporting, evaluation of response and updating of subject contact information. An effort should be made to perform all activities conducted on visit Day 84.

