6.2.8. Unscheduled Visit

Unscheduled visits will be performed upon investigator's discretion, upon Sponsor request to redo tests with unusual results or complete missing results and may occur upon subject's decision with no notification in advance. Unscheduled visits will include any study procedure deemed necessary, as described in Section 6.1.

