7.3. PREMATURE DISCONTINUATION FROM STUDY

Study will be prematurely discontinued in any of the following cases:

- Subject's request.
- Any life-threatening AE may cause prematurely discontinuation.
- Systemic hypersensitivity reaction may cause premature discontinuation.
- Any serious or severe ADR (defined in Section 9.3) clinically evaluated by the PI and/or Sponsor as warranting subject discontinuation.
- Non-compliance: Subject's non-compliance with study procedures as evaluated by PI and/or Sponsor as warranting subject discontinuation.
- Other reasons regarded by PI as warranting subject's discontinuation.
- Premature study termination as described in Section 7.4.

Subjects who discontinue the study prematurely will be queried whether an AE contributed to their decision

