9.1.2. Definition of Serious Adverse Event

A SAE is defined as any AE occurring at any dose that results in any of the following outcomes:

- death
- a life-threatening AE, as defined below
- subject hospitalization or prolongation of existing hospitalization
- a persistent or significant disability/incapacity
- a congenital anomaly/birth defect
- important medical event, as defined below

A life-threatening AE is any AE that places the subject, in the view of the investigator, at immediate risk of death from the reaction as it occurred (i.e., it does not include a reaction that, had it occurred in a more severe form, might have caused death).

An important medical event is an AE that may not result in death, be life-threatening, or require hospitalization but may be considered a serious AE when, based upon appropriate medical judgment, may jeopardize the subject and may require medical or surgical intervention to prevent one of the outcomes listed above. It can also include AEs otherwise judged to be serious by either the investigator or the Sponsor.

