11. DATA COLLECTION, STUDY MONITORING, AND DATA DISCLOSURE

11.1. DATA COLLECTION AND REPORTING

Each study subject will be assigned an individual CRF that will contain all of the relevant study information. The investigator shall ensure that all data is completely and accurately recorded on the CRFs throughout trial duration.

Data reported on the CRF that are derived from source documents should be consistent with the source documents or the discrepancies should be explained.

All fields and blanks in the CRFs will be completed. The following abbreviations are to be used when values or answers are not available: NA = Not applicable, ND = Not done, UNK = Unknown, CONT = Continued.

Any change or correction to a CRF should be dated, initialed, and explained (if necessary) and should not obscure the original entry (i.e., an audit trail should be maintained). If an entry on a CRF form is changed, the correction will be made as follows: A single line will be drawn through the incorrect entry, the date and initials of the reporting individual will be added beside the entered change and/or correction, and an explanation will be added when applicable.

When a subject withdraws from the study, regardless of cause, all final study evaluations should be attempted.

If a subject is lost to follow-up, (i.e., fails to return for scheduled visits) every reasonable effort must be made to contact the subject in order to determine why the subject failed to return. All actions taken in this regard will be documented and dated in the CRF.

Once completed, a copy of each completed CRF will be signed and dated by the investigator or a designated representative and submitted to the Sponsor.

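### Section 5.4 forces withdrawal for an undefined serious side effect; with a single dosing day this stops no exposure and puts on-schedule follow-up at risk, chiefly the only post-treatment MRI

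*Combined protocol and SAP*

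**What the plan says.** **Withdrawal rules**

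- Section 5.4: "Subjects experiencing serious side effect will be withdrawn from the study, but followed until the event resolves or becomes stable". It adds: "If a subject is withdrawn or removed from the study due to serious side effects, the subject will not be replaced". The section's heading concerns withdrawals that are not due to intolerable side effects, which does not fit this text.
- Section 7.3 lists, among the grounds for discontinuing a subject: "Any serious or severe ADR (defined in Section 9.3) clinically evaluated by the PI and/or Sponsor as warranting subject discontinuation". A life-threatening AE or a systemic hypersensitivity reaction is listed only as something that may lead to discontinuation.
- Section 3.3.2 asks the investigator to consider discontinuation whenever an SAE occurs. It also requires that the skin of such subjects be followed, without giving visit days.
- Section 9.1.2 supplies the nearest defined term: "A SAE is defined as any AE occurring at any dose that results in any of the following outcomes". Serious side effect is defined nowhere.

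**What happens after withdrawal**

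- Section 6.2.7, on the termination visit: "An effort should be made to perform all activities conducted on visit Day 84".
- Section 11.1: "When a subject withdraws from the study, regardless of cause, all final study evaluations should be attempted".
- Section 6.2.8 allows unscheduled visits, among other reasons "upon Sponsor request to redo tests with unusual results or complete missing results".
- Section 9.5.1 requires ADRs to be followed to resolution, with a limit of 6 months after injection.
- Section 10.4.1 keeps withdrawn subjects in the safety set. Section 10.6 rules out imputation.

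**Dosing and imaging**

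- Sections 3.3.1 and 6.2.3.1: one dose, given as multiple injections on Day 0.
- Sections 6.1.9 and 6.1.15.2.2: MRI at screening and at Day 84 ± 5 days only.

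**The concern.** Withdrawal for safety normally protects a subject from further drug. Here there is no further drug to withhold, so the only thing that withdrawal can change is observation. A subject with an important safety outcome is the one whose later course a safety study most needs to see on schedule, yet 5.4 takes that subject off the schedule, does not replace them, and leaves gaps that will not be filled by imputation. Any missing data would then be related to outcome.

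The three sections also give different instructions for one event. A site that follows 5.4 must withdraw the subject; a site that follows 7.3 or 3.3.2 decides case by case. Because the 5.4 trigger is undefined, two sites could also differ on which events count.

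**Working it through.** The plan states no figure on this point, so there is none to reproduce. The check is a comparison of texts, followed by simple counts for scale.

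**Step 1. Who decides.** Under 5.4 nobody does: the event leads to withdrawal. Under 7.3 the PI and/or sponsor decides. Under 3.3.2 the investigator considers it (I read that sentence as concerning the subject, since it asks for CRF documentation). The rules cannot all be followed whenever the judgement is that the subject can stay.

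**Step 2. Exposure avoided.** Doses planned after Day 0 = 0. Exposure prevented by withdrawal = 0.

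**Step 3. What is still collected after withdrawal.**

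- Required, but on no visit schedule: the event itself (5.4), the skin after an SAE (3.3.2), ADRs (9.5.1).
- Best effort: Day 84 procedures at a termination visit (6.2.7), final evaluations (11.1).
- Discretionary: unscheduled visits (6.2.8).
- Required at Day 28, 56 or 84 in a withdrawn subject: nothing. In particular, no text requires the MRI at Day 84 ± 5.

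**Step 4. Scheduled assessments at risk (Appendix I).** The timing of withdrawal is assumed, for illustration.

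- After the Day 14 visit: skin grades 3 (Days 28, 56, 84) + FACE-Q 3 + physician's assessment 3 + MRI 1 = 10.
- After the Day 28 visit: 2 + 2 + 2 + 1 = 7.
- The skin grades are partly protected by Step 3. Without them the counts are 10 − 3 = 7 and 7 − 2 = 5.
- A termination visit can recover one assessment of each kind, but off schedule.

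**Step 5. Timing of a termination MRI.** The window opens on Day 84 − 5 = Day 79. If the scan were done on the assumed day of withdrawal, it would precede the window by 79 − 14 = 65 days or 79 − 28 = 51 days. Section 6.2.7 fixes no day for the termination visit, so these are examples. Such a scan would not be at the endpoint's time point.

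**Step 6. Weight of one subject.**

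- Cohort 1 active, 8 subjects (3.1): 1/8 = 12.5%.
- Cohort 2 active: with at least 4 placebo, at most 16 − 4 = 12 active; a 2:1 ratio gives 16 × 2/3 = 10.7, so 10 or 11. One subject is therefore 1/12 = 8.3% to 1/10 = 10%.

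**The case against.** The strongest reply is that little is lost. Follow-up of the event, of the skin after an SAE, and of ADRs is required, not optional. Withdrawn subjects stay in the safety set and data already collected are kept. The analysis that 10.5.4 names for the primary safety endpoint is the incidence of treatment-related SAEs, and withdrawal does not remove the triggering event from it. Efficacy is secondary, mainly descriptive (10.5.1) and not powered (10.3). All of this stands, and it is why the point is minor.

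It can also be said that the contrast between sections is softer than it looks. Section 7.3 opens in mandatory terms, the SAE definition itself contains medical judgement, and the mismatch between the 5.4 heading and its text suggests leftover drafting. That is fair as to intent. But the safety items in 7.3 are each conditional and the sentence in 5.4 is not, so a site reading 5.4 literally would withdraw the subject.

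Three stronger readings are tempting and are not supported:

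- *That the data would be lost.* Sections 6.2.7, 6.2.8 and 11.1 give routes to collect them, so they are at risk, and skin data less so than the rest.
- *That inflammation would spoil an early MRI.* The background in 1.1.1 describes prominent inflammation in pigs at 14 days, but nothing says that it distorts MRI fat volume. In humans, MRI showed reduction at Day 28 (1.1.1; not statistically significant per 1.2.4.1.1), and the largest reduction in the 180 mg cohort was at Day 56 (1.2.4.1.2). Those were abdominal sites, but they show that an earlier scan can be informative. The sound objection is only that it is at the wrong time for this endpoint.
- *That the event rate can be taken as zero in the 54 subjects exposed so far.* The statement in 3.2 concerns dose per site, spacing and maximal dose; it is not an SAE count for 54 subjects. Lipedema results were pending (1.2.4.1.3), a severe ALT elevation occurred in the first trial (1.2.4.1.1), 240 mg is untested, and the 5.4 trigger is undefined.

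**Conclusion.** The concern holds as a minor one. Section 5.4, followed as written, withdraws a subject without reducing exposure and conflicts with the judgement-based rules in 3.3.2 and 7.3. The consequence is possible loss of on-schedule data: part of the skin grading, FACE-Q, the physician's assessment and, most of all, the single post-treatment MRI.

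Few subjects are likely to be affected, but this is a judgement; no rate can be derived from the documents. The rule applies equally to both treatments. One affected active subject carries the weight shown in Step 6, which is enough to matter to a small descriptive summary but not to the trial's safety conclusion. The conclusion assumes that sites apply 5.4 literally and that a termination visit takes place near the time of withdrawal.

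**What to change.** In Section 5.4, replace serious side effect with *SAE (Section 9.1.2)*, and replace the mandatory withdrawal with:

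*An injected subject with an SAE, or meeting a Section 7.3 safety criterion, remains on the scheduled visits to Day 84, including MRI at Day 84 ± 5, unless consent is withdrawn or the investigator judges a specific procedure medically unsuitable.*

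Amend to match the safety items in 7.3 (life-threatening AE, systemic hypersensitivity, serious or severe ADR) and the sentence in 3.3.2 on discontinuation after an SAE. Aligning 5.4 with 7.3 alone would still let a subject leave the schedule. Medical management of the event does not change.

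The cost is a protocol amendment with sponsor and IRB/EC approval (7.5). No visits or procedures are added, because the visits and the Day 84 MRI are already planned for every subject.
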